9.2.1.1.3. Symptoms

In the acute phase, concussion is an evolving injury with rapidly changing clinical signs and symptoms [2].

These symptoms can be categorized into [1–3, 6, 7]:

- Somatic symptoms, such as:
 - Headache
 - Vision changes including blurred vision, light sensitivity, difficulty reading and convergence dysfunction
 - Coordination disorders
 - Disturbance in balance
 - Insomnia
 - Somnolence
 - Drowsiness

| | | |
|--------|---|--|
| RGnCON | Clinical Investigation Plan Version 2.0 - 11 August 2022 | |
|--------|---|--|

- Cognitive impairment, such as:
 - Feeling like in a fog
 - Disorientation
 - Difficulty concentrating
 - Slowed reaction time
 - Loss of consciousness
 - Amnesia
 - Neurological deficit
- Emotional / behavioral changes such as:
 - Irritability
 - Lability

Altogether, this set of symptoms is called **concussion syndrome** [1, 6].

In adults, symptoms typically resolve in 10 to 14 days [2]. However, some may linger for weeks. Persistent post-concussion syndrome occurs when symptoms persist beyond 3 months [6].

Of note, well-trained and well-prepared sportspersons are thought to heal more rapidly [1, 4].

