- For the evolution of executive function, the following timepoints will be compared: (D0 before treatment – D7 after treatment) and a mixed effect regression model will be used with a patient random effect. Group effects (5 Hz vs 10Hz), period effects and group-by-period interaction will be added as fixed effects. The stratification variables will be added in the model as covariates.
 - TMT A: time (s)
 - TMT A: number of errors
 - TMT B: time (s)
 - TMT B: number of errors
 - TMT B-A: time (s)
 - TMT B-A: number of errors
- For concussion syndrome symptoms (SCAT5): For the analysis at D0 before treatment, D7 before treatment, D14 and D52, a mixed linear regression model will be used with a patient random effect. Group effects (5 Hz vs 10Hz), period effects and group-by-period interaction will be added as fixed effects. The stratification variables will be added in the model as covariates. This model will be run for:
 - The total number of symptoms (score from 0 to 22)
 - The symptom severity (score from 0 to 132)

| | | |
|--------|---|---|
| RGnCON | Clinical Investigation Plan Version 2.0 - 11 August 2022 |  |
|--------|---|---|

- A description analyses of blood markers at each time point and the change from baseline to each time point will be assessed by groups and overall.

Sensitivity analysis:

A sensitivity analysis will be conducted on the secondary performance endpoints in the FAS without excluding any data that would be collected after intercurrent events.

Of note, data of patients with a second concussion that occurred after RGn550 first treatment session will be considered before the onset of the concussion. Similarly, data of patients with a contraindication to RGn550 that occurred after RGn550 first treatment session will be considered before the onset of the contraindication.

This sensitivity analysis will be performed only if the proportion of excluded patients exceeds 10% (at least 5 patients excluded).

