## 8.4. Safety analysis

### 8.4.1. Analysis of the primary safety endpoint: proportion of patients with at least one ADE after use of RGn550

The proportion of patients with at least one ADE after use of RGn550 in acute concussion syndrome, either at a frequency of 5 or 10 Hz, will be calculated along with its 95% confidence interval (using exact Clopper-Pearson method). This analysis will be performed on the FAS population, by treatment groups and overall.

The following template will be used.

	RGn550 5Hz N=xx	RGn550 10Hz N=xx	Total N=xx
At least one ADE			
Non-missing	xx	xx	xx
Yes [n (%) 95% CI]	xx (xx.x) xx.x ; xx.x	xx (xx.x) xx.x ; xx.x	xx (xx.x) xx.x ; xx.x
No [n (%) 95% CI]	xx (xx.x) xx.x ; xx.x	xx (xx.x) xx.x ; xx.x	xx (xx.x) xx.x ; xx.x
missing	xx	xx	xx

Note: a lost to follow-up rate of 10% is anticipated. If this rate is higher, an analysis of the primary endpoint using percentage of patient-years will be considered.

Note: at the time of writing this SAP version, a data review has been performed showing that the lost-to-follow-up rate is 0%.

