#### 8.5.1.1. Automated oculomotor and oculopostural functions and balance function

For the evolution of parameters of oculomotor and oculopostural functions and balance function defined in Section 0, the following timepoints will be compared: (D0 after treatment - D0 before treatment, D7 before treatment - D0 before treatment, D7 after treatment - D0 before treatment, and D52 – D0 before treatment). A mixed effect regression model (logistic model for a categorical parameters and a linear model for continuous parameters) will be used with a patient random effect. Group effects (5 Hz vs 10Hz), period effects (D0 before, D0 after, D7 before, D7 after and D52) and the group-by-period interaction will be added as fixed effects. The stratification variable gender (male/female) will be added in the model as covariates.

Note: the stratification variable concussion history within 6 months prior to inclusion (yes/no) will not be added in the model as too few patients had concussion history (cf. data review minutes of 18/07/2023).

The following template will be used for continuous parameters.

	Group of treatment		
Ref = D0 before treatment	RGn550 5Hz N=xx	RGn550 10Hz N=xx	Difference
Endpoint XXX at D0 after treatment			
Adjusted mean	x.xx	x.xx	x.xx
95% CI	x.xx ; x.xx	x.xx ; x.xx	x.xx ; x.xx
p-value	.	.	0.xxx
Endpoint XXX at D7 before treatment			
Adjusted mean	x.xx	x.xx	x.xx
95% CI	x.xx ; x.xx	x.xx ; x.xx	x.xx ; x.xx
p-value	.	.	0.xxx
Endpoint XXX at D7 after treatment			
Adjusted mean	x.xx	x.xx	x.xx
95% CI	x.xx ; x.xx	x.xx ; x.xx	x.xx ; x.xx
p-value	.	.	0.xxx
Endpoint XXX at D52			

		Group of treatment		
Ref = D0 before treatment		RGn550 5Hz N=xx	RGn550 10Hz N=xx	Difference
Adjusted mean		x.xx	x.xx	x.xx
95% CI		x.xx ; x.xx	x.xx ; x.xx	x.xx ; x.xx
p-value		.	.	0.xxx

From an mixed model including treatment (p=0.xxx), visit (p=0.xxx), treatment-by-visit interaction (p=0.xxxx) as fixed effects and variable xxx as random effect, variableyyy (p=0.xxx) as baseline covariate.

The following template will be used for categorical parameters.

	RGn550 10Hz vs RGn550 5Hz at visit 1	RGn550 10Hz vs RGn550 5Hz at visit 2	visit 2 vs visit 1 at RGn550 10Hz	visit 2 vs visit 1 at RGn550 5Hz
Endpoint XXX				
Odds ratio	X.X	X.X	X.X	X.X
95% CI	[X.X ; X.X]	[X.X ; X.X]	[X.X ; X.X]	[X.X ; X.X]

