### 8.5.1.3. Concussion syndrome symptoms (SCAT5)

For concussion syndrome symptoms (SCAT5) functions defined in Section 0, the following timepoints will be analyzed (D0 before treatment, D7 before treatment, D14 and D52), a mixed linear regression model will be used with a patient random effect. Group effects (5 Hz vs 10Hz), period effects and

group-by-period interaction will be added as fixed effects. The stratification variables and SCAT5 baseline will be added in the model as covariates.

The same template as above will be used.

In addition, for exploratory purpose, the concussion syndrome symptoms (SCAT5) will also be analyzed in the subgroup “Number of previous concussions”.

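### The SCAT5 model uses the D0 score as both response and covariate and names no contrast: one reading miscalibrates the standard error, and in the other the baseline adjustment has no effect

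*SAP*

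**What the plan says.** SAP 8.5.1.3 states that "the following timepoints will be analyzed (D0 before treatment, D7 before treatment, D14 and D52), a mixed linear regression model will be used", with a random patient effect and fixed effects for group, period and their interaction. It then adds: "The stratification variables and SCAT5 baseline will be added in the model as covariates". The only SCAT5 taken before the first session is the one at D0 (Protocol Table 2), so the baseline covariate and the D0 response are the same number.

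Sections 8.5.1.1 and 8.5.1.2 write out which timepoints are compared. Section 8.5.1.3 names no contrast and reuses the earlier template. That template is headed "Ref = D0 before treatment", which suggests change from D0. Its rows, such as "Endpoint XXX at D7 before treatment", hold an adjusted mean per arm and a difference, which reads as the arm difference at that visit.

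The protocol's SCAT5 model (9.6.3.2) has no baseline term: "The stratification variables will be added in the model as covariates. This model will be run for" the two SCAT5 scores. SAP Section 10 does not list the added covariate and says that nothing beyond its list has changed.

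A separate wording point: 8.5.1.3 keeps both stratification variables, whereas 8.5.1.1 says that concussion history "will not be added in the model as too few patients had concussion history", and 8.5.1.2 likewise uses gender only.

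**The concern.** In every D0 row the response equals its covariate, so those rows fit too well and pull the common baseline slope towards 1. What this does to the reported result depends on a contrast that the plan leaves open. A programmer could follow either the template's heading or its rows, and neither choice gives both a calibrated test and a working baseline adjustment.

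SCAT5 is the only patient-reported performance endpoint, and the template prints a p-value for 5 Hz against 10 Hz at each visit. Protocol 9.2.3 says the two-arm design is meant to show which frequency is better, so these p-values are likely to be read for that purpose.

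**Working it through.** **Inputs.** From the documents: 50 patients randomised 1:1, so 25 per arm; four SCAT5 visits; two-sided alpha 0.05; random patient intercept; one baseline slope. Assumed, because the documents give no SCAT5 SD or correlation: scores in units of the D0 SD, multivariate normal, equal correlation ρ = 0.3, 0.5 or 0.7 between visits, complete data, no true arm difference, gender left out. The plan states no SCAT5 figure to reproduce. Its one design figure concerns ADEs (1 − 0.96^50 = 0.87) and is correct.

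**Reading (a): arm difference at a visit, equal variances.** The random-intercept model estimates the slope by regressing the patient's four-visit mean on D0. D0 predicts itself with slope 1 and the other three visits with slope ρ, so b = (1 + 3ρ)/4 instead of ρ. The adjusted variance is 1 − 2bρ + b² at a post-baseline visit and (1 − b)² at D0. The model assigns every visit the average of the four. SE ratio = √(average / post-baseline variance); type I error = 2{1 − Φ(1.96 × ratio)}.

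| ρ | b | post-baseline variance | D0 variance | average | SE ratio | type I error |
|---|---|---|---|---|---|---|
| 0.3 | 0.475 | 0.941 | 0.276 | 0.774 | 0.907 | 7.5% |
| 0.5 | 0.625 | 0.766 | 0.141 | 0.609 | 0.892 | 8.0% |
| 0.7 | 0.775 | 0.516 | 0.051 | 0.399 | 0.880 | 8.5% |

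Simulation at 25 per arm (20,000 trials per scenario, Satterthwaite degrees of freedom) gives ratios 0.91/0.89/0.88 and type I error 7.3–8.4%. A separate set of 8,000 trials per scenario gives 7.6–9.1%. Without the baseline covariate, the same at-visit difference gives 4.7–5.1% and 5.1–5.6% respectively. Under equal variances the duplicated D0 is therefore the cause. The overall treatment p-value in the template footnote is not affected (4.7–5.2%).

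**Reading (b): arm difference in change from D0, equal variances.** For any slope b, (Y − b·D0) − (D0 − b·D0) = Y − D0, so the covariate drops out. In simulation the estimate was identical with and without it in every dataset. The SE was also identical unless the patient variance was estimated at zero (largest relative change 6%, at ρ = 0.3). Type I error is 4.9–5.2%. Relative to a real baseline adjustment, the variance is 2(1 − ρ)/(1 − ρ²) = 2/(1 + ρ) = 1.54/1.33/1.18. At ρ = 0.5 the SE is √(2/25 × 1) = 0.283 against √(2/25 × 0.75) = 0.245.

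**If variance falls.** This is plausible, since Protocol 9.2.1.1.3 says "In adults, symptoms typically resolve in 10 to 14 days". Take SD 1, 0.8, 0.6, 0.3 at D0, D7, D14, D52 and ρ = 0.5 under reading (a):

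- b = (1 + 0.4 + 0.3 + 0.15)/4 = 0.4625.
- Adjusted variances are 0.289, 0.484, 0.296 and 0.165; their average is 0.309.
- SE ratios are √(0.309/0.484) = 0.80 at D7, 1.02 at D14 and 1.37 at D52, so type I error is about 12%, 4.6% and 0.7%.

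Simulated over the three ρ values:

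| SD pattern | reading (a) D7 | D14 | D52 | reading (b), all visits |
|---|---|---|---|---|
| 1, 0.9, 0.8, 0.7 | 9.4–10.7% | 6.4–7.1% | 4.0–5.1% | 5.3–7.6% |
| 1, 0.8, 0.6, 0.3 | 10.6–11.8% | 3.8–4.5% | 0.4–2.1% | 7.0–11.7% |

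A further case with SD 25, 15, 10, 6 and autoregressive correlation 0.6 gives 4.8%, 3.3% and 2.0% at D7, D14 and D52 under reading (a). The direction of the error thus depends on the pattern.

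**After the fix.** Visit-wise ANCOVA, which stands in for the unstructured model with D0-by-visit when data are complete, gives 4.7–5.2% at every visit in all nine combinations of three SD patterns and three correlations.

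**The case against.** Four counter-arguments deserve weight.

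1. *The larger error rates belong to the constant-variance random intercept, which the protocol already specified.* For change from D0 this is almost wholly right. Under the strong fall at D7, one comparison gives 11.1/9.0/7.2% for the SAP model and 10.4/8.7/7.0% for the protocol model. For the at-visit difference, removing D0 from the responses while keeping the random intercept raises the D7 error to 13.3–13.7%. The part attributable to the duplicated D0 alone is the equal-variance result under reading (a).
2. *A third reading exists: D0 as covariate and reference only.* The template has no row for D0 before treatment and its footnote provides for a baseline covariate. Under equal variances that model is calibrated (5.1–5.3%). But 8.5.1.3 explicitly lists D0 among the analysed timepoints, so this is not what the text says.
3. *Data may not be complete.* SAP 8.4.1 reports that "a data review has been performed showing that the lost-to-follow-up rate is 0" per cent, which is not the same as no missing forms: the D14 form is filled in at home and returned at D52. This stands. With missing visits the cancellation in reading (b) is only approximate.
4. *The stakes are small and the inputs assumed.* SCAT5 is a secondary endpoint in a pilot with no multiplicity adjustment, and bounded scores near zero will not be normal. This limits the importance and the precision of the figures, but it does not make the specification coherent.

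**Conclusion.** The specification is wrong as written. D0 is used twice, no contrast is named, and the departure from the protocol's model is not declared; these three points rest on the text alone.

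The size rests on the stated assumptions. With equal variances, reading (a) gives a type I error of about 7.5–8.5% in place of 5%. Reading (b) gives a valid test whose claimed baseline adjustment has no effect when data are complete. With falling variance both readings are miscalibrated by amounts that vary with visit and pattern, and much of that comes from the random intercept and not from the duplication. The effect is confined to the SCAT5 comparison between arms. It should be fixed, but it does not touch the primary ADE analysis.

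**What to change.** In SAP 8.5.1.3, take D7, D14 and D52 as the responses. Include D0 SCAT5, D0-by-visit, group, visit, group-by-visit and gender as fixed effects. Replace the random intercept with an unstructured within-patient covariance; dropping D0 from the responses is not enough by itself if variance changes over time. State that the reported contrast is the adjusted arm difference at each visit.

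The minimum alternative is to delete the baseline covariate, return to the protocol's model and name the contrast. That restores calibration only under equal variances: under the strong fall, the at-visit type I error would be 7.5–8.0% at D7 and 0.0% at D52.

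Either way, use the same stratification covariate as 8.5.1.1 and record the departures from the protocol's model in Section 10. The cost is SAP wording and a few lines of SAS code; no new data are needed.

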**Note:**

An additional analysis for oculomotor and oculopostural functions, balance function, executive function (TMT A&B) and concussion syndrome symptoms (SCAT5) will be performed on all patients to evaluate the change between D0 and D52. A mixed effect regression model (logistic model for a categorical parameter and a linear model for continuous parameters) will be used with a patient random effect and a period effect (D0 and D52) will be added as fixed effects.

### 8.5.1.4. Blood markers

A descriptive analysis of blood markers defined in Section 0, at each time point and the change from baseline will be assessed by randomization arms and overall.

The following template will be used.

		Value at visit										Change from baseline						
		Missing	N	Mean	SD	Median	Q1	Q3	Min	Max	Mean	SD	Median	Q1	Q3	Min	Max	
RGn550 5Hz	Baseline	xx	xx	xx	xx	xx	xx	xx	xx	xx	xx	xx	xx	xx	xx	xx	xx	
	D52	xx	xx	xx	xx	xx	xx	xx	xx	xx								
RGn550 10Hz	Baseline	xx	xx	xx	xx	xx	xx	xx	xx	xx	xx	xx	xx	xx	xx	xx	xx	
	D52	xx	xx	xx	xx	xx	xx	xx	xx	xx								
Total	Baseline	xx	xx	xx	xx	xx	xx	xx	xx	xx	xx	xx	xx	xx	xx	xx	xx	
	D52	xx	xx	xx	xx	xx	xx	xx	xx	xx								

In addition, for exploratory purpose, the Blood markers will also be analyzed in the subgroup “Number of previous concussions”.

### 8.5.1.5. Sensitivity analysis

A sensitivity analysis will be conducted on the secondary performance endpoints (oculomotor and oculopostural functions, balance function, executive function (TMT A&B) , concussion syndrome symptoms (SCAT5) and blood markers) in the FAS without excluding any data that would be collected after intercurrent events.

Of note, data of patients with a second concussion that occurred after RGn550 first treatment session will be considered before the onset of the concussion. Similarly, data of patients with a contraindication to RGn550 that occurred after RGn550 first treatment session will be considered before the onset of the contraindication.

This sensitivity analysis will be performed only if the proportion of excluded patients exceeds 10% (at least 5 patients excluded).

## 8.6. Exploratory analyses

Exploratory analyses will be performed on the potential relationship between drowsiness (AE) and concussion severity parameters (measured by the SCAT5 score) using a chi-square or Fisher exact test, for the qualitative variables, and a Student or Mann Whitney (Kruskal-Wallis) test, depending on the normality of parameters, for the quantitative variables.

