Following this, the patient will evaluate his/her symptoms using the **SCAT5 symptom evaluation tool**. The patient will rate the intensity of every symptom from 0 (none) to 6 (severe) using a form. This will allow to calculate the total number of symptoms (out of 22) and the symptom severity score (out of 132) (see Appendix 12.3).

A **blood sample** will also be obtained from the patients by a nurse. The blood sample analysis will be performed by Montpellier Neuroscience Institute (*Institut de Neuroscience de Montpellier*) following the institute standard practice.

During the visit, the patients will be **randomized** in a 1:1 ratio to the 5 Hz group or 10 Hz group using the centralized Interactive Web Response System (IWRS) incorporated into the eCRF. A block randomization method will be used. Only patients will be blinded to their assigned treatment.

Depending on their assigned group, the patients will then be **treated** with one of the 5 Hz RGn550 devices or one of the 10 Hz RGn550 devices for 20 min. To perform the treatment, the principal investigator will follow the below instructions:

- Make the patient comfortable.
- Install the helmet on the patient's head, taking care not to bump it with the modules.
- Lightly tighten the soft helmet holding wire and check the positions of the modules. Each module can be moved slightly to adjust its position.
- On the control unit, in the menu on the left, choose the option 'Program' and choose the proposed treatment
- Finally press the red arrow to start the treatment.

A countdown is displayed on the screen indicating the time remaining until the end of the treatment session. At each treatment session, the principal investigator will fulfil a treatment sheet associated with the used device and mention the number of the treated patient, date of treatment, number of

treatment session and duration of treatment. To stop the treatment, the principal investigator will press the red button with a cross inside that is displayed on the screen (a confirmation message will be displayed to avoid any manipulation error).

Following treatment, the investigators will:

- **Perform the following tests** following the methodology described above:
 - NPC
 - Cover test
 - Maddox rod test
 - Static stabilometric test
- **Collect any AEs and DDs** that occurred during the visit.

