9.13.3. Safety Reporting to Sponsor

Per Article 80 of the European Regulation 2017/745, the following events shall be recorded:

- Any AE of a type identified in the CIP as being critical to the evaluation of the results of that clinical investigation
- Any SAEs
- Any DD that might have led to a SAE if appropriate action had not been taken intervention had not occurred, or circumstances had been less fortunate
- Any new findings in relation to the above events.

The following events that occur in patients included in RGnCON from inclusion to the end of the 52-day follow-up period will thus be recorded:

- All AEs, including SAEs
- All DDs
- Any new findings in relation to AEs and DDs.

AEs will be reported using the Adverse Event form of the eCRF while DDs will be reported using the Device Deficiency form. The date of the event, its severity, causality, treatment and resolution will notably be collected.

These events will be reported immediately to REGEnLIFE and no later than 3 calendar days after the investigator becomes aware of the event.

If needed, the investigations site team or [REDACTED] can contact REGEnLIFE's materiovigilance department via email ([contact]) or phone ([contact]).

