12.2. Trail Making Test

12.2.1. Part A

12.2.2. Part B

12.3. SCAT5 Symptom Evaluation Tool

**ÉTAPE 2: ÉVALUATION
DES SYMPTÔMES**

Vous devez donner le formulaire des symptômes à l'athlète et lui demander de lire ce paragraphe d'instructions à voix haute avant de remplir l'échelle. Pour l'évaluation de base, l'athlète doit donner une note à ses symptômes selon son ressenti habituel. Pour l'évaluation post-traumatisme, l'athlète doit donner une note à ses symptômes actuels.

Cochez la case correspondante: Base Post-traumatisme

Donnez le formulaire à l'athlète

| | RAS | Léger | Modéré | Important | | |
|--|-----|-------|--------|-----------|-----|---------|
| Maux de têtes | 0 | 1 | 2 | 3 | 4 | 5 6 |
| «Pression dans le crâne» | 0 | 1 | 2 | 3 | 4 | 5 6 |
| Douleur dans le cou | 0 | 1 | 2 | 3 | 4 | 5 6 |
| Nausée ou vomissement | 0 | 1 | 2 | 3 | 4 | 5 6 |
| Vertiges | 0 | 1 | 2 | 3 | 4 | 5 6 |
| Vision trouble | 0 | 1 | 2 | 3 | 4 | 5 6 |
| Problèmes d'équilibre | 0 | 1 | 2 | 3 | 4 | 5 6 |
| Sensibilité à la lumière | 0 | 1 | 2 | 3 | 4 | 5 6 |
| Sensibilité au bruit | 0 | 1 | 2 | 3 | 4 | 5 6 |
| Sensation d'être ralenti.e | 0 | 1 | 2 | 3 | 4 | 5 6 |
| Sensation d'être «dans le brouillard» | 0 | 1 | 2 | 3 | 4 | 5 6 |
| «Ne pas se sentir normal.e» | 0 | 1 | 2 | 3 | 4 | 5 6 |
| Problèmes de concentration | 0 | 1 | 2 | 3 | 4 | 5 6 |
| Problèmes de mémoire | 0 | 1 | 2 | 3 | 4 | 5 6 |
| Fatigue ou manque d'énergie | 0 | 1 | 2 | 3 | 4 | 5 6 |
| Confusion | 0 | 1 | 2 | 3 | 4 | 5 6 |
| Somnolence | 0 | 1 | 2 | 3 | 4 | 5 6 |
| Sensibilité | 0 | 1 | 2 | 3 | 4 | 5 6 |
| Irritabilité | 0 | 1 | 2 | 3 | 4 | 5 6 |
| Tristesse | 0 | 1 | 2 | 3 | 4 | 5 6 |
| Nervosité ou anxiété | 0 | 1 | 2 | 3 | 4 | 5 6 |
| Difficultés à s'endormir (si applicable) | 0 | 1 | 2 | 3 | 4 | 5 6 |
| Nombre total de symptômes: | | | | | | sur 22 |
| Degré de sévérité des symptômes: | | | | | | sur 132 |
| Vos symptômes s'aggravent-ils pendant une activité physique? | | | | | 0 N | |
| Vos symptômes s'aggravent-ils pendant une activité mentale? | | | | | 0 N | |
| Si 100 % correspond à une sensation normale, à combien de pour cent vous sentez-vous normal.e? | | | | | | |

Si la réponse n'est pas 100%, pourquoi?

Rendez le formulaire à l'examinateur.trice

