- Concussion syndrome symptoms (SCAT5) will be used as recorded in the eCRF at D0 before treatment, D7 before treatment, D14 and D52
  - Symptom severity score
  - The total number of symptoms
- Blood markers at D0 before treatment to D52 will be used as recorded in the eCRF
  - Anti-inflammatory cytokines InterLeukin (IL)-1 receptor antagonist, IL-4, IL-6, IL-10, IL-11 and IL-13
  - S100 calcium binding protein B (S100B)

- Glial Fibrillary Acidic Protein (GFAP)
- Ubiquitin C-terminal Hydrolase-L1 (UCH-L1).

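### The exploratory drowsiness analysis (SAP 8.6) uses a SCAT5 total that contains a drowsiness item and fixes no SCAT5 visit, so the association may be partly circular

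*SAP*

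**What the plan says.** SAP 8.6 plans this: "Exploratory analyses will be performed on the potential relationship between drowsiness (AE) and concussion severity parameters (measured by the SCAT5 score"). The methods are listed as "using a chi-square or Fisher exact test, for the qualitative variables, and a Student or Mann Whitney (Kruskal-Wallis) test", chosen by variable type and normality. It names no SCAT5 visit, removes no item, and does not require the score to precede the event. SAP section 10 declares the analysis as an addition to the protocol.

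The SCAT5 measures come from SAP 6.2.2: "Concussion syndrome symptoms (SCAT5) will be used as recorded in the eCRF at D0 before treatment, D7 before treatment, D14 and D52". Only two are defined, the "Symptom severity score" and the total number of symptoms. Protocol 9.5.5.1 explains how they arise from the item ratings: "This will allow to calculate the total number of symptoms (out of 22) and the symptom severity score (out of 132").

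The form in Protocol Appendix 12.3 contains the line "Somnolence | 0 | 1 | 2 | 3 | 4 | 5 6" and, as a separate item, "Fatigue ou manque d'énergie". Both feed both totals.

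Protocol 9.13.3 records adverse events "from inclusion to the end of the 52-day follow-up period". Protocol 9.2.1.1.3 lists somnolence and drowsiness among the symptoms of concussion itself.

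**The concern.** The analysis asks whether patients who reported drowsiness as an adverse event had a more severe concussion. The severity measure already contains a drowsiness rating, so part of any association could be drowsiness related to itself.

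The open visit makes this worse. If SCAT5 is taken at D7, D14 or D52, a drowsy episode that began after a session may be recorded as an adverse event and also raise the SCAT5 total. The score then measures the event instead of preceding it.

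What is at stake is interpretation. With no sham arm, a reader may use this analysis to judge whether drowsiness belongs to the concussion or to the device. A partly circular association would be weak evidence for that judgement.

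**Working it through.** **1. The plan's own figure.** The only sample-size figure is the probability of at least one ADE in 50 patients at an ADE probability of 0.04 (Protocol 9.6.1). Check: 1 − 0.96^50 = 0.870, which agrees with the stated 0.87. No figure is given for SAP 8.6.

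**2. Size of the overlap.** The drowsiness item supplies at most 6 of 132 severity points (4.5%) and 1 of 22 symptoms (4.5%). If items were independent with equal variance, its correlation with the total would be 1/√22 = 0.21. Adding fatigue gives 12/132 = 9.1% and √(2/22) = 0.30.

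**3. Timing.**

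| SCAT5 visit | Can the score include an episode that began after a session? |
|---|---|
| D0 before treatment | No |
| D7 before treatment | Yes, after session 1 |
| D14 and D52 | Yes, after either session |

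At D0 before treatment, the only overlap left is drowsiness already present at baseline.

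**4. Symptom count.** An item adds 0 or 1 to the count. Its contribution to the group difference d is the difference in the proportion of patients with the item, so it cannot exceed 1. Assumed inputs, absent from the documents: n1 = 10 or 15 of 50 with the event, and SD of the count 4 to 8. The rejection rate is that of a two-sided 5% t test with 48 df and non-centrality d / (SD·√(1/n1 + 1/n2)). Example: d = 0.5, SD = 4, n1 = 15 gives 0.5 / (4 × 0.309) = 0.405 and a rate of 0.068.

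| Difference d through one item | Rejection rate |
|---|---|
| 0.3 | 0.051–0.057 |
| 0.5 | 0.053–0.068 |
| 1 (maximum) | 0.064–0.125 |

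With 2 of 50 patients affected (0.04 × 50, borrowing the plan's ADE probability), the maximum d = 1 gives 0.053–0.063.

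**5. Consistency of those SDs.** Twenty-two independent 0/1 items have an SD of at most √(22 × 0.25) = 2.35. From SD² = 5.5(1 + 21ρ), an SD of 4 needs an average inter-item correlation ρ of at least (16/5.5 − 1)/21 = 0.09, and an SD of 8 needs (64/5.5 − 1)/21 = 0.51. SDs of this size therefore imply correlated items.

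**6. Severity score, item-level simulation.** Settings: 50 patients, 22 items scored 0–6, Mann-Whitney test at two-sided 0.05, 1,500 repeats (Monte Carlo standard error √(0.05 × 0.95/1500) = 0.006). The event occurs in 10%, 20% or 40% of patients and depends on the drowsiness item only. All other items are independent of it.

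| Correlation among the other items | Full severity score | Symptom count |
|---|---|---|
| 0 | 0.103, 0.130, 0.147 | 0.048, 0.069, 0.116 |
| 0.1 | 0.061, 0.079, 0.089 | 0.049, 0.064, 0.069 |
| 0.3 | 0.052, 0.057, 0.063 | 0.054, 0.053, 0.065 |
| 0.5 | 0.051, 0.066, 0.054 | 0.061, 0.061, 0.057 |

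The score without the drowsiness and fatigue items rejected in 0.044–0.057 of these runs, which is nominal. Removing drowsiness alone must have the same effect here, because the event is generated independently of every other item. If fatigue is also tied to drowsiness (correlation 0.6), the full severity score rejects in 0.183–0.297 at correlation 0, 0.093–0.167 at 0.1, and 0.059–0.091 at 0.3 or more.

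**The case against.** The case for leaving SAP 8.6 alone has several parts.

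- **Drowsiness is part of concussion.** Protocol 9.2.1.1.3 says so, and the standard SCAT5 total is the recognised score. A reader might infer that the overlap can produce an association with no link to severity at all. That goes too far, because drowsiness at D0 is itself part of severity as SCAT5 defines it. What can be said is that the association may not extend to the other symptoms.
- **Large false-positive rates are not supported.** A reader might take a difference of one or two symptoms as typical; with the assumptions in step 4, two symptoms would give 0.107–0.355. One symptom from one item requires every affected patient and no unaffected patient to have it, and two symptoms require this of fatigue as well. On the severity score, a 6-point shift from drowsiness alone would require every affected patient to rate it 6 and everyone else 0. The documents give no drowsiness event rate, SCAT5 SD or inter-item correlation.
- **Fatigue is a separate item** and need not count as overlap.
- **The direction is not certain.** Drowsiness seen before treatment may be regarded as pre-existing and not recorded as an event, which would weaken the association.
- **The primary endpoint is untouched.** A reader might infer that this analysis can remove a device signal. ADEs are counted by the relationship recorded in the eCRF (SAP 6.2.1), a missing relationship counts as related (SAP 7.5), and SAP 8.6 reclassifies nothing.

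All of this limits the size and the consequence. It does not answer the two plain facts: the score contains the item, and the visit is not fixed.

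**Conclusion.** The point holds as a minor one. SAP 8.6 relates a drowsiness event to a total that includes drowsiness, and it leaves open whether that total precedes the event.

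The inflation cannot be sized from the documents. Under the assumptions shown, it is modest at most for the single overlapping item: about 5–15% rejection against a nominal 5%, and near nominal if the other items are correlated at 0.3 or more. The higher simulated rates depend on treating fatigue as overlap and on weakly correlated items.

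The consequence is confined to how an exploratory result is read.

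**What to change.** In SAP 8.6:

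- Name the D0 before-treatment SCAT5 number of symptoms and severity score as the severity measures. This rules out counting a post-treatment episode twice.
- Report the same tests with the Somnolence item removed (21 items; maximum 21 symptoms and 6 × 21 = 126 points) beside the full score. This deals with the baseline overlap.
- Show the baseline Somnolence rating separately, by drowsiness event status.
- Removing fatigue as well (20 items, maximum 120) is optional.

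No new patient assessment is needed. The cost is a little more analysis and a non-standard score shown beside the standard one. SAP 6.2.2 mentions only the totals, so if the eCRF holds no item ratings, they would have to be entered from the completed D0 forms, about 50 at the planned sample size.
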